# 6.5.4 Dose delay/modification for hematological adverse events due to SAR440234

If a patient experiences hematologic AEs (e.g. decreased neutrophil count, decreased platelet count, febrile neutropenia, or anemia) related to the underlying hematologic malignancy or baseline cytopenias and the investigator and Sponsor agree that continuing treatment is safe, the patient will continue treatment with SAR440234 without dose delay and/or modification.

If the AE does not appear to be related to the underlying hematologic malignancy or baseline cytopenias, dose delay and/or modification must be applied as in the following.

# Decreased neutrophil count Grade 4, decreased platelet count Grade 4, or febrile neutropenia Grade 3 and Grade 4, and anemia Grade 4:

- If the AE resolves before the time of the next schedule infusion or within ≤10 days after the last infusion, treatment will be given as planned after recovery with dose reduction by 1 step.
- If the AE resolves in 10 to 14 days after the last infusion, omit 1 dose. After recovery, treatment will resume with dose reduction by 1 step, and will restart with the lead-in dose.
- If the AE persists >14 days after the last infusion, a bone marrow aspirate will be performed.
  - If <3 infusions of SAR440234 have been administered, the study treatment will be permanently discontinued,
  - If ≥3 infusions of SAR440234 have already been administered, the patient will resume the study treatment, once the AE has resolved, if there is perceived benefit, and the Investigator and Sponsor agree. Dose reduction by 1 step must be applied, and treatment will resume with the lead-in dose.

# Bone marrow hypocellularity Grade 4 for at least 14 days

- The infusion(s) must be omitted until recovery of hypocellularity to baseline or Grade ≤1 and will be documented by a bone marrow aspirate.
- If bone marrow hypocellularity resolves in ≤21 days after the last infusion (ie, 2 doses omitted), treatment will resume with dose reduction by 1 step, and will resume with the lead-in dose.
- If bone marrow hypocellularity persists for >21 days after the last infusion, the following guidelines apply:
  - If <3 infusions of SAR440234 have been administered, the study treatment will be discontinued permanently,
  - If ≥3 infusions of SAR440234 have already been administered, the patient will resume the study treatment, once the AE has resolved, if there is evidence of clinical benefit, and the Investigator and Sponsor agree. Dose reduction by 1 step must be applied, and treatment will resume with the lead-in dose.

Guidelines for the resumption of treatment following treatment interruption secondary to hematological AEs are summarized in Table 7 and Table 8.

Table 7 - Dose delays and modifications for hematological adverse events

Adverse Event	Condition to		Duration of Adverse	e Event
	Continue Treatment	Resolved in ≤10 days after last infusion	Resolved in 11 to 14 days after last infusion	Persists >14 days after last infusion
Grade 4 decreased neutrophil count	Recovery to Baseline or	Administer as planned after recovery. Dose	Omit 1 dose. After AE resolved, restart	If <3 infusions administered before onset of AE, then
Grade 4 decreased platelet count	Grade ≤1	reduction by 1 step.	treatment. Dose reduction by 1 step	permanent discontinuation a If >3 infusions administered
Grade 3 or Grade 4 febrile neutropenia Grade 4 anemia			and restart treatment with the lead-in dose. Do not escalate past	before onset of AE, then resume when AE has resolved, if there is evidence of
Grade 4 anemia			the target dose.	clinical benefit. Dose reduction by 1 step and restart treatment with the lead-in dose.

a If permanent discontinuation is mandated but there is evidence of clinical benefit and the AE has resolved, study treatment may continue if the Investigator and the Sponsor agree

AE=adverse event

Table 8 - Dose delays and modifications for bone marrow hypocellularity Grade 4

Adverse Event	Condition to	Duration of Adverse Event		
	Continue Treatment	Resolved in ≤21 days after last infusion	Persists >21 days after last infusion	
Grade 4 bone marrow hypocellularity	Recovery to Baseline or Grade ≤1	Omit doses until recovery. Dose reduction by 1 step and restart treatment with the lead-in dose. Do not escalate past the target dose.	If <3 infusions administered before onset of AE, then permanent discontinuation a If ≥3 infusions administered before onset of AE: omit 1 dose. Restart treatment when AE has resolved, if there is evidence of clinical benefit. Dose reduction by 1 step and restart treatment with the lead-in dose.	

a If permanent discontinuation is mandated but there is evidence of clinical benefit and the AE has resolved, study treatment may continue if the Investigator and the Sponsor agree
 AE=adverse event

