# 4.5.3 SAR440234 dose and regimen

A dose escalation single agent trial will be initiated in patients with R/R AML, HR-MDS, and B-ALL. This trial is intended to establish proof-of-concept for this drug, based on clinical, pharmacokinetic, and biomarker evaluation; to assess the safety and preliminary anti-leukemia activity of SAR440234; and to define the optimal dose of drug as a single agent.

Use of intra-patient dose escalation is proposed. This dosage strategy has already demonstrated its benefit in approved drugs, such as Blincyto®, with the same objective of cytokine release syndrome (CRS) mitigation. The strategy of intra-patient dose escalation is currently being used for other drugs under development.

In the first 2 dose levels (DL1 and DL2), SAR440234 will be administrated once weekly. After evaluation of the first 2 dose levels, a 2-step dosing increase in the first week of administration will be implemented to reach higher exposure in a shorter time frame.

A weekly schedule (bi-weekly during Cycle 1, Week 1 in DL  $\geq$ 3) will be evaluated with drug administration on Days 1, 4 (DL  $\geq$ 3 only), 8, 15, 22, 29, and 36 of a 6-week cycle that will be repeated, provided that the patient is achieving clinical benefit.

29-Aug-2019 Version number: 2

Cycles run consecutively so that Day 1 of each cycle is normally 7 days after the start of the last infusion in the previous cycle. If bone marrow hypocellularity Grade 4 or hematological toxicity Grade 3 or 4 is diagnosed, the interval between doses must be extended until toxicity is resolved. If the interval between doses is or exceeds 10 days, the treatment must be restarted with the lead-in doses appropriate for the selected dose level.

Systematic premedication with the corticosteroid, dexamethasone (two doses of 20 mg IV), and leukotriene inhibitor montelukast (one dose of 10 mg by mouth) are planned starting with the first dose of SAR440234 tested. Dexamethasone and/or tocilizumab will be used to treat Grade ≥2 CRS, as described below and in Section 6.7. Dexamethasone has been chosen because it penetrates the blood-brain barrier (20).

Use of intra-patient dose escalation is proposed. This dosage strategy has already demonstrated its benefit in approved drugs, such as Blincyto®, with the same objective of CRS mitigation. The strategy of intra-patient dose escalation is currently being used for other drugs under development, as well.

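### Section 6.5.4, Table 8 and Section 4.5.3 of the protocol do not agree on when infusions are held for Grade 4 bone marrow hypocellularity

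*Protocol*

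**What the plan says.** Protocol Section 6.5.4 deals with hematological adverse events that do not appear to come from the underlying malignancy or baseline cytopenias. Its hypocellularity rule stands under the heading "Bone marrow hypocellularity Grade 4 for at least 14 days". Under that heading the action is: "The infusion(s) must be omitted until recovery of hypocellularity to baseline or Grade ≤1". The text then splits at 21 days after the last infusion, and the shorter branch carries a dose count: "If bone marrow hypocellularity resolves in ≤21 days after the last infusion (ie, 2 doses omitted". The preceding block of Section 6.5.4 covers neutrophils, platelets, febrile neutropenia and anemia, but not hypocellularity.

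The text refers to Tables 7 and 8 as its summary. The second is titled "Table 8 - Dose delays and modifications for bone marrow hypocellularity Grade 4" and names no minimum duration. For events resolved within 21 days it says "Omit doses until recovery. Dose reduction by 1 step and restart treatment with the lead-in dose". Beyond 21 days it separates two cases: "If <3 infusions administered before onset of AE, then permanent discontinuation" (subject to a footnote exception) and "If ≥3 infusions administered before onset of AE: omit 1 dose", followed in the same cell by restart once the event has resolved.

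Section 4.5.3 states the trigger a third time, from diagnosis: "If bone marrow hypocellularity Grade 4 or hematological toxicity Grade 3 or 4 is diagnosed, the interval between doses must be extended until toxicity" has resolved.

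Section 6.5 sets the default: planned doses are given unless an adverse event warrants a modification.

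**The concern.** A summary table should not drop the condition that switches its rule on. A site working from the 6.5.4 text finds no hypocellularity instruction for the first 14 days and falls back on the Section 6.5 default. A site working from Table 8 or Section 4.5.3 holds at once. Two patients with the same event can therefore be treated differently.

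Two things are at stake. The first is patient safety, since the passages differ on whether a patient with a Grade 4 marrow event receives further study drug. The second concerns the primary dose-escalation analysis. DLT evaluability depends on the number of Cycle 1 infusions received (Protocol Sections 6.3 and 13.3.2; SAP Table 3), and non-evaluable patients are replaced. In cohorts of 3 to 6, one patient moving in or out matters.

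Separately, a single omitted dose for an event lasting more than 21 days does not fit weekly dosing.

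**Working it through.** **Inputs.** Dosing interval of 7 days (Section 6.5.2). Infusion window of plus or minus 1 day (Section 6.5.1). DLT evaluability at 5 of 6 infusions in DL1 and DL2, and 6 of 7 in DL3 and above (Sections 6.3 and 13.3.2). The last infusion is day 0, so the next weekly slots are days 7, 14, 21 and so on.

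**The plan's own figure.** Resuming on day 21 means the day 7 and day 14 slots were missed, which is 2 doses. This reproduces the count in the text as the maximum for that branch; resumption on day 14 would miss 1.

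**The trigger, side by side.**

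| Place | Applies to | Days 0 to 14 of the event |
|---|---|---|
| 6.5.4 text | Grade 4 lasting 14 days or more | No instruction |
| Table 8 | Any Grade 4 | Hold until recovery |
| Section 4.5.3 | Grade 4 once diagnosed | Extend the interval until resolved |

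**Infusions at stake.** With onset on day *o*, count the weekly slots *d* with *o* < *d* < *o* + 14:
- onset on day 0: slot 7 only, because on day 14 the 14-day condition is already met. Count = 1.
- onset on days 1 to 6: slots 7 and 14. Count = 2.
- onset on day 7: slot 14 only. Count = 1.

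So 1 to 2 weekly infusions depend on the passage followed. This count is for the 7-day part of the schedule and leaves aside the extra Day 4 infusion in DL3 and above.

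**DLT evaluability in Cycle 1.** Take a patient with no DLT on any criterion and no other missed dose.
- One infusion held: 6 − 1 = 5, which meets 5 of 6; 7 − 1 = 6, which meets 6 of 7. Evaluable on this count.
- Two held: 6 − 2 = 4, below 5; 7 − 2 = 5, below 6. Not evaluable, and replaced (Sections 6.3 and 11.2).
- None held: 6 of 6 or 7 of 7. Evaluable.

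The two-dose case can occur without meeting the hypocellularity DLT criterion. With onset on day 3, slots 7 and 14 are held; recovery by day 16 is within 14 days of onset; dosing resumes on day 21.

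**The branch beyond 21 days with 3 or more infusions given.** The third infusion falls on Day 15 in DL1 and DL2 and on Day 8 in DL3 and above. Every planned gap after it is 7 days, so the Day 4 infusion does not alter the count. By day 22 the slots on days 7, 14 and 21 have passed: 3 doses missed. If the day 21 dose is given on day 22 within the +1-day window, the count is 2. It cannot be 1.

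**The case against.** The strongest reply is that Section 6.5.4 never tells a site to infuse during the first 14 days. A reader might infer that it does, but the text is only silent, and the restriction comes from a heading. Section 4.5.3 can be said to fill the gap with a mandatory extension from diagnosis, in line with Table 8, leaving one heading out of step. This stands as a limit on the point: the conflict is between a rule with a duration condition and two without one, not between an order to dose and an order to hold. It does not remove the point, because the operating section still carries the condition and the Section 6.5 default applies where no modification is called for.

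A second reply is that few cases would arise. Scheduled on-treatment marrow in Cycle 1 is only at Day 42 (within 2 days), close to the end of the 42-day DLT window. Earlier detection would probably follow a severe cytopenia, for which Table 7 already requires recovery before dosing if the event is attributed to the drug. That is a fair limit on frequency, though additional aspirates are also provided for when clinically indicated.

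A reader might also infer that continued infusions would impair marrow recovery, and so alter the DLT count and the MTD. The documents contain nothing from which to show that. Nor does the 14-day figure in the DLT definition (Section 6.2.1) settle the matter: it classifies an event and does not say when to hold.

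Finally, a reader might take the single omitted dose in Table 8 as leave to restart during an unresolved event. The same cell restarts only on resolution, and the table's condition column requires recovery to baseline or Grade 1 or less. The phrase also covers only patients with 3 or more infusions.

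**Conclusion.** The inconsistency is real and is in the current text. The trigger for holding infusions differs between the 6.5.4 heading on one side and Table 8 and Section 4.5.3 on the other. At stake are 1 to 2 weekly infusions per event in its first 14 days. In Cycle 1, holding 2 rather than 0 moves a patient without a DLT from evaluable to replaced; holding 1 does not change status on the infusion count. This rests on weekly dosing, held doses not being made up, no other missed infusion, and an event attributed to study drug.

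The conclusion stops there. It does not extend to a shown effect on recovery, the DLT rate or the MTD, and the number of affected patients cannot be estimated from the documents. The dose count in the branch beyond 21 days is an editorial error that changes no patient's treatment.

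**What to change.** Reconcile the hold trigger so that the 6.5.4 heading, Table 8 and Section 4.5.3 say the same thing, including what applies to a Grade 4 event in its first 14 days. Which trigger to adopt is for the sponsor and its clinical experts. In the same edit, bring the omitted-dose wording in Table 8's column beyond 21 days (3 or more infusions) into line with the text's omission until recovery.

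The cost is wording in two sections and one table, with no change to sample size or analysis method. The SAP records early termination of the trial. If no further dosing is planned, the study report could instead state which reading was applied to any patient with Grade 4 hypocellularity, using the dose-omission and Cycle 1 DLT listings that the SAP already plans.

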# 6.5.5 Dose delay/modification for other adverse events not including hematological adverse events or cytokine release syndrome due to SAR440234

Resolution of an AE requires recovery to baseline or Grade  $\leq 1$ .

If the AE is related to the underlying hematologic malignancy or baseline cytopenias and the investigator and Sponsor agree that continuing treatment is safe, the patient will continue treatment with SAR440234 without dose delay and/or modification.

If the AE does not appear to be related to the underlying hematologic malignancy or baseline cytopenias, dose delay and/or modification must be applied as in the following.

For patients with AEs that are not hematological and/or not CRS or infusion-related reactions, the administration of SAR440234 should be modified as follows:

#### Grade 1:

• Continue treatment as planned.

### Grade 2:

- If the AE is resolved before the time of the next scheduled infusion, or within ≤10 days after the last infusion, treatment will continue without change after recovery.
- If the AE is resolved >10 days after the last infusion, omit 1 dose. After recovery, treatment will restart with the lead-in dose (Section 6.5.2) as appropriate to achieve the same step that was administered prior to the onset of the AE.
- If the patient experiences a third episode of the same AE, the study treatment will be permanently discontinued.

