# **Study continuation**

The duration of each cycle of treatment is 42 days, with weekly administration of IMP (except for Cycle 1 Week 1 in DL  $\geq$ 3 when 2 administrations will be given).

The criteria for retreatment of patients are described in Section 6.5.

The dose given in the second or subsequent cycles will be the last dose given in the previous cycle. If there is a  $\geq$ 10-day interval between administrations of SAR440234, the next infusion must start with the lead-in doses appropriate for the selected dose level.

Additional pharmacokinetic data, safety and disease response will be assessed as indicated in the flow charts (Section 1.2) and when clinically indicated.

A Study Committee including the main Investigators, Sponsor's clinical team, and ad hoc experts, when appropriate, will regularly review the safety data, and will make recommendations as appropriate. The Study Committee will also decide the RP2D, including the recommended lead-in dose and schedule, for the Expansion Part in R/R AML and HR-MDS patients.

Additional (optional) cohort(s) beyond DL8, or intermediate dose levels, may be evaluated; the decision to proceed with these optional cohort(s), however, will be discussed with the Study Committee and will be based on the available safety, exploratory, and pharmacokinetic data.

It is anticipated that the number of patients enrolled in the Dose Escalation Part will be 30 to 40.

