# 6.5.1 Dose delays

If any infusion (excluding Day 4 infusion) cannot be made on the scheduled day, a time window of +1 or -1 day is allowed. Subsequent infusions should be administered according to the regular weekly schedule.

**Dose delay of \geq 3 days:** If the infusion is administered  $\geq 3$  days later than planned, dosing must restart with the lead-in dose (Table 4).

If a Day 4 infusion cannot be made on the scheduled day: The infusion will be made on the next possible day, keeping a 4-day interval before the next infusion. If the infusion cannot be administered within 10 days of the last infusion, dosing must restart with the lead-in dose (Table 4).

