#### Grade 4:

- The next infusion will be omitted.
- If the AE resolves in ≤14 days after the last infusion, if there is perceived benefit, and the Investigator and Sponsor agree, treatment will restart with the lead-in dose. Dose reduction by 1 step will be applied.
- If the AE is not resolved in ≤14 days after the last infusion, treatment will be permanently discontinued.
- If the patient experiences a second episode of the same AE, the study treatment will be permanently discontinued.

Guidelines for the resumption of treatment following treatment interruption secondary to AEs other than hematological AEs, CRS, or infusion-related reactions are provided in Table 9.

Table 9 - Dose delay and dose modification for adverse events not including hematological adverse events, cytokine release syndrome, or infusion-related reactions

Grade	Condition	Dur	ation of adverse e	vent	Second	Third
	to Continue Treatment	Resolved in <10 days after last infusion	Resolved in 10 to 14 days after last infusion	Persisting >14 days after last infusion	Episode	Episode
1	Not applicable		No change		No change	No change
2	Recovery to Baseline or Grade ≤1	Administer as planned on recovery with dose as planned.	Omit 1 dose Restart after AE resolved. Treatment will restart with the lead-in dose. May escalate to planned dose level.	Omit 1 dose. Restart after AE resolved. Treatment will restart with the lead-in dose. May escalate to planned dose level.	Allowed. Same recommend- ation as for first episode.	Permanent discontinua- tion a
3	Recovery to Baseline or Grade ≤1	Administer as planned on recovery. Dose reduction by 1 step.	Omit 1 dose. Restart after AE resolved. Dose reduction by 1 step and treatment will restart with the lead-in dose. Do not escalate past target dose.	Permanent discontinuation a	Permanent discontinua- tion a	Not applicable
4	Recovery to Baseline or Grade ≤1	Restart after AE re clinical benefit. Tre with dose reductio the lead-in dose. I	1 dose. solved if evidence of atment restart will be on by 1 step and with Do not escalate past et dose.	Permanent discontinuation a	Permanent discontinua- tion a	Not applicable

a If permanent discontinuation is mandated but there is evidence of clinical benefit and the AE has resolved, study treatment may continue if the Investigator and the Sponsor agree

AE=adverse event

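### For a Grade 2 non-hematological AE that resolves exactly 10 days after the last weekly infusion, Section 6.5.5 and Table 9 give different restart instructions, and the Grade 3 and hematological text put that day in two bands

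*Protocol*

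**What the plan says.** Days below are counted from the last infusion.

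- **Section 6.5.5, Grade 2 text.** An AE resolved "within ≤10 days after the last infusion, treatment will continue without change after recovery". The next bullet reads "If the AE is resolved >10 days after the last infusion, omit 1 dose", followed by a lead-in restart.
- **Table 9, which summarizes the same section.** The first column covers resolution in fewer than 10 days. The second is headed "Resolved in 10 to 14 days after last infusion", and its Grade 2 entry is "Omit 1 dose Restart after AE resolved. Treatment will restart with the lead-in dose. May escalate to planned dose level".
- **Section 6.5.5, Grade 3 text.** The first bullet runs up to and including 10 days, with a 1-step reduction. The second covers 10 to 14 days, with one dose omitted, a 1-step reduction and lead-in.
- **Section 6.5.4, hematological text.** It has the same two overlapping bands. Table 7 cuts at 10 days or fewer, then 11 to 14 days.
- **General lead-in rules.** Section 4.5.3: "If the interval between doses is or exceeds 10 days, the treatment must be restarted with the lead-in doses". Section 6.2.2 (Study continuation) says that after an interval of 10 days or more "the next infusion must start with the lead-in doses appropriate for the selected dose level". Section 6.5.1 sets its trigger by lateness, at 3 or more "days later than planned, dosing must restart with the lead-in dose (Table 4"). Section 6.5.2 allows a dose without lead-in after a 2-day delay, which it equates to fewer than 10 days from the last infusion.

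**The concern.** A site with a Grade 2 non-hematological AE that resolves on Day 10 finds two current instructions in one section. One continues treatment unchanged. The other omits a dose and goes back to lead-in. For a Grade 3 AE or a listed hematological AE, the text itself offers two actions for that day.

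Section 6.2.1 gives the purpose of within-patient escalation as lowering the risk of severe CRS, and this is a first-in-human T-cell engager. The Grade 2 text read in isolation is the least protective version: same dose, nothing omitted and no lead-in mentioned.

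Sites could also treat the same patient differently. In Cycle 1 that bears on who counts as evaluable for dose-limiting toxicity, because Section 13.3.2 tolerates one missed administration (5 of 6, or 6 of 7). This last step is an inference; the documents do not work it through.

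**Working it through.** The protocol states no figure to reproduce. The check sets the cut-points side by side and evaluates them around Day 10.

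**Day count, weekly schedule.** Last infusion = Day 0; next infusion due = Day 7.

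- Day 9: 9 − 7 = 2 days late, interval under 10 days. Section 6.5.2 allows dosing without lead-in.
- Day 10: 10 − 7 = 3 days late, interval 10 days. Lead-in is required by Sections 4.5.3 and 6.2.2 (interval of 10 days or more) and by Section 6.5.1 (3 or more days late).

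**Instruction by day of AE resolution**

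| Source | Day 9 | Day 10 | Day 11 |
|---|---|---|---|
| 6.5.5 Grade 2 text (≤10 / >10) | no change | **no change** | omit 1 dose, lead-in |
| Table 9, Grade 2 (<10 / 10–14) | as planned | **omit 1 dose, lead-in** | omit 1 dose, lead-in |
| 6.5.5 Grade 3 text (≤10 / 10–14) | 1-step reduction | **both bands** | omit 1 dose, 1-step reduction, lead-in |
| Table 9, Grade 3 (<10 / 10–14) | 1-step reduction | omit 1 dose, 1-step reduction, lead-in | same as Day 10 |
| 6.5.4 text (≤10 / 10–14) | 1-step reduction | **both bands** | omit 1 dose, 1-step reduction, lead-in |
| Table 7 (≤10 / 11–14) | 1-step reduction | 1-step reduction, no lead-in stated | omit 1 dose, 1-step reduction, lead-in |

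**Reading the table**

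- *Grade 2.* Text and table agree on Days 9 and 11 and disagree only on Day 10. The Table 9 heading is unlikely to be an extraction error, because its next column starts at 10.
- *Grade 3 and hematological text.* The two bands share Day 10. The 1-step reduction is common to both; omission and lead-in are not.
- *Table 7.* It is internally clean, but its cut-point differs from that of the text it summarizes. It does not mention lead-in at Day 10, yet Section 4.5.3 requires it.
- *Grade 4 non-hematological AEs.* Unaffected: text and Table 9 both omit a dose when the AE resolves within 14 days.

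**What the general rules settle.** They require lead-in at a 10-day interval. None requires a dose to be omitted, so omission at Day 10 is unresolved.

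**The case against.** The strongest reply is that the safety-relevant part is already covered. Three mandatory rules, two of them in Section 6, require lead-in at Day 10. Unchanged treatment in the Grade 2 text can be read as an unchanged dose, and nothing there waives lead-in. This stands. A reader might infer that the protocol authorizes restarting on Day 10 without lead-in; taken as a whole, it does not.

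A reader might also infer that the general rules back Table 9 in full. They back it on lead-in only. Section 6.5 describes modifications as set out in the text and summarized in the tables. That is not a precedence clause, but if anything it favors the text, so Table 9 does not automatically win on omission. For hematological AEs, Table 7 and the first bullet of Section 6.5.4 both include Day 10 in the as-planned band. Imposing an omission there would be a clinical change that the documents do not call for.

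Three nearby places may look like further contradictions but are not:

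- The Day 4 clause of Section 6.5.1 ("If the infusion cannot be administered within 10 days of the last infusion, dosing must restart with the lead-in dose") does not name Day 10, but the 10-day rule in Section 6.2.2 covers it.
- An AE resolved by Day 9 with the infusion given on Day 10 or later falls under an AE band and the interval rule. Both apply together.
- The 10-day delay wording in Section 12.1 adds a lead-in and hospitalization condition. It does not bear on the Day 10 bands.

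What survives is the Day 10 conflict between text and table for Grade 2, and the overlap within the Grade 3 and hematological text. No general rule removes either.

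**Conclusion.** The protocol is wrong as written, for one day. At Day 10 on the weekly schedule, the Grade 2 text and Table 9 cannot both be followed. The Grade 3 text and the Section 6.5.4 text each point to two actions. Lead-in is settled by the general rules, and the Grade 2 wording read alone conflicts with them; omission of a dose is not settled.

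The severity is minor to moderate. Premedication applies whichever instruction is followed, CRS and infusion reactions have their own rules in Section 6.5.3, and the 1-step reduction applies in both Grade 3 bands and both hematological bands. No effect on dose can be stated, because the doses in Table 4 are not visible. No primary endpoint or decision rule is shown to change. The SAP (Section 4.3) records early termination, which limits the practical consequence but does not make the text consistent.

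The conclusion assumes a planned 7-day interval and the current protocol text.

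**What to change.** - **Section 6.5.5, Grade 2 text:** change the bands to <10 days and ≥10 days, as in Table 9.
- **Section 6.5.5, Grade 3 text:** change the lower band to <10 days and keep 10 to 14 days for the next. Table 9 is unchanged.
- **Section 6.5.4 and Table 7:** remove the Day 10 overlap so that text and table share one cut-point. Whether a dose is omitted at Day 10 for hematological AEs is the sponsor's choice.
- **Add to Sections 6.5.4 and 6.5.5:** *In addition to any lead-in required elsewhere, lead-in is mandatory whenever the actual interval between infusions is ≥10 days.*

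The added sentence must not be turned around to say that an interval under 10 days removes lead-in. All other triggers stay in force, including lead-in after omitted doses in Tables 5, 6, 8 and 9 and at 3 or more days late in Section 6.5.1. At dose level 3 and above, for example, the Day 8 infusion is planned 8 − 4 = 4 days after the Day 4 infusion. Three days late is then 4 + 3 = 7 days after the last infusion, and Section 6.5.1 already requires lead-in there.

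The cost is cut-point wording in two sections and, depending on the sponsor's choice, Table 7, plus one repeated sentence. No new data or procedures are needed.
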